1.1 Metastatic spinal cord compression

Metastatic spinal cord compression (MSCC) is a feared complication of metastases to the vertebra. Approximately 5-10 percent of patients with metastatic cancer experience MSCC, most commonly patients with lung-, breast-, prostate and renal cancer.¹ MSCC is a disabling condition that can lead to pain, disablement of sensory and motor function distal to the injury.² Early detection and onset of treatment is key to improve outcome results. Diagnosis is typically set through either CT or MRI scan; however, MRI is the preferred modality for diagnosing.³ Symptoms are severe, unremitting pain, progressive discomfort, sensory symptoms, function deficits and bladder or bowel dysfunction⁴. Treatment is mainly high dose steroids to decrease edema and radiotherapy. Surgery is offered, when possible, to patients in good performance status and followed by radiotherapy². Interventions mainly aim at pain relief and preserving motor functions. A small fraction of patients with highly chemo-sensitive tumors are offered chemotherapy.⁴ The performance status at the time of diagnosis is the main determining factor of the post-treatment outcomes, with patients with lower-extremity function and sensation at the onset of treatment having a longer survival time⁴. When MSCC is diagnosed, life expectancy is typically short, with a 2-year survival of approximately 10% and a median survival of less than 6 months.^{2,5} As treatment is palliative Quality of Life (QoL) is important, however, patients may experience early toxicity after radiotherapy, paradoxically causing reduced QoL.^{5,6}

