3.3 Sample size calculation for primary endpoint

We assume that we can decrease maximum esophageal dose from 30 Gy to 10 Gy and that this will result in a 50% decrease in risk of early esophageal toxicity.¹¹ We want to conduct a phase III trial with 1:1 randomization between standard VMAT and experimental esophageal VMAT. Prior data

indicate that the rate of early esophageal toxicity with standard VMAT is 0.6. ¹¹ If the true early esophageal toxicity rate in the esophagus sparing VMAT arm is 0.3, conventional power calculation indicates that we would need to include 62 patients in each arm, to be able to reject the null hypothesis that the toxicity rates for experimental and control arms are equal with a probability (power) of 0.9. The Type I error probability associated with the test of this null hypothesis is 0.05 and calculations are performed assuming Fisher's exact test. However, with this patient population we anticipate high rate of heterogeneity and we need to account for loss of follow-up due to patients dying early or being too frail. We increase the study size to 100 patients in each arm to account for these challenges. Patients will be stratified according to performance status and fractionation scheme.

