Data are reported by the patient in a paper-edition trial diary, by electronic questionnaires or by telephone consultations. Survival data, re-irradiation, and hospitalization data are derived from patient's treatment records. After the results of an interim analysis revealing low compliance (1), weekly CTC registrations were implemented for all patients in the first 5 weeks after treatment start (from patient No. 107).

Table 1. Follow-up schedule in the ESO-SPARE trial

	Treatment start	Daily	Weekly	Weekly
		1-5 weeks	1-5 weeks	1-9 weeks
PRO-CTC-AE: Dysphagia, nausea, dyspepsia	X	X		
CTC-AE 5.0*	X		X	
EORTC-QLQ-C30 and EQ-5D-5L	X			X
Medication: Analgesics, corticosteroids, antiemetics	X			
Weight	X			X

*Starting from patient No. 107

Estimated Enrollment: 200 patients.

Allocation: Patients are randomized 1:1 to either esophagus-sparring treatment or standard treatment. Patients are stratified by center and fractionation. Randomization is performed in REDCap using random allocation with a block size of four and six.

Masking: Single-blind. Patients are blinded to randomization outcome.

Study Start Date: May 2021

Estimated Primary Completion Date: April 2024

Study Completion Date: The last patient will be included on April 30, 2024, or after the inclusion of 200 patients, whichever comes first.

Timing of final analysis

Following study closure, nine weeks of follow-up after radiotherapy start will be allowed for all patients, at which point data will be collected for primary end-point analysis. Analysis of data in respect to secondary endpoints and exploratory studies might be analyzed at any point of time, at the discretion of the study group.

Data

Data are captured in REDCap. Data will be kept in databases 10 years after the last patient is included.

[Sample size](#)

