We assume that we can decrease maximum esophageal dose from 30 Gy to 10 Gy and that this will result in a 50% decrease in risk of early esophageal toxicity. We want to conduct a phase III trial with 1:1 randomization between standard VMAT and experimental esophageal VMAT. Prior data (2) indicate that the rate of early esophageal toxicity with standard VMAT is 0.6. If the true early esophageal toxicity rate in the esophagus sparing VMAT arm is 0.3, conventional power calculation indicates that we would need to include 62 patients in each arm, to be able to reject the null hypothesis that the toxicity rates for experimental and control arms are equal with a probability (power) of 0.9. The Type I error probability associated with the test of this null hypothesis is 0.05 and calculations are performed assuming Fisher's exact test. However, with this patient population we anticipate high rate of heterogeneity, and we need to account for loss of follow-up due to patients dying early or being too frail. We increase the study size to 100 patients in each arm to account for these challenges. Patients will be stratified according to fractionation scheme and treating center.

Ambulatory function as a co-primary endpoint

We wish to demonstrate that the improvement in esophageal toxicity does not come at a price of reduced effect of the radiation. As a prioritized secondary endpoint, we choose ambulatory function (preserved ability to walk) measured on a 4-point scale. We assume that the conventional arm follows the distribution of the SCORAD trial and test our ability to detect a difference from an assumed inferior experimental arm in terms of ambulatory function, see Table 2.

If the underlying “true” distribution on ambulatory grades is as depicted in the table and we assume 66 patients per arm are evaluable, we find that 84% of simulated trials would lead to statistically significant differences detected with a Wilcoxon rank sum test for comparing the trial arms. In other words, the power of the trial is enough to detect a deterioration according to the able, which would lead to rejection of the experimental treatment.

The power of ESO-SPARE is enough to detect a difference in ambulatory function as seen in Table 2

	Conventional arm	Experimental arm
Grade 1: Ambulatory without the use of walking aids	22	11
Grade 2: Ambulatory with walking aids	44	32
Grade 3: Unable to walk	26	37
Grade 4: Absence or flicker of motor power in any muscle group	8	20

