Table 2: Distribution of ambulatory function. The conventional arm follows the SCORAD trial (Hoskin et al., 2019).

Recruitment, withdrawal, and follow-up

Enrollment, intervention, allocation, follow-up, and data analysis will be summarized in a CONSORT diagram in accordance with CONSORT 2010 guidelines (4)

Statistical principles

Confidence intervals and P values

Level of significance: $p < 0.05$ with no adjustment for multiplicity. Confidence intervals are reported at 95 % limits (bound by zero) and calculated by the binominal distribution for rates and as per Kaplan-Meier method for time-to-event analyses.

Analysis

We will report our data in accordance with the CONSORT 2010 guidelines including the CONSORT Patient-Reported Outcome (PRO) extension (4,5) .

Analyses will be performed per-protocol for all patients who have received any study treatment.

Primary analysis of NCI-PRO-CTC-AE toxicity will only include weeks where ≥ 3 days questionnaires are completed.

Primary analysis of EQ-5D-5L and EORTC-QLQ-C30 will only include completed questionnaires.

All CTC-AE and PRO-CTC-AE grades will be reported.

Missing data will be described in detail, see missing data section.

A. Co-primary endpoints

1. Peak dysphagia (difficulty swallowing) measured by NCI-PRO-CTC-AE within 5 weeks after start of radiotherapy (daily measurements).

PRO-CTC-AE responses are scored from 0 to 4, with 0 representing "None" and 4 representing "Very severe". For each patient the peak value within 5 weeks after start of radiotherapy (daily measurements) will be included in the analysis. Difference in scores between treatment arms will be compared using Wilcoxon rank-sum test.

2. Ambulatory function measured by EQ-5D-5L mobility dimension at 9 weeks after start of radiotherapy.

EQ-5D-5L measures individual generic health status using 5 dimensions: mobility, self-care, usual activities, pain/discomfort, and anxiety/depression. Each dimension has 5 levels depending on the severity of symptoms, with 1 representing “No problems” and 5 representing “Extreme problems”. Difference in scores between mobility dimension treatment arms will be compared using Wilcoxon rank-sum test.

B. Severity of dysphagia, nausea and dyspepsia measured by NCI-PRO-CTC-AE [Time Frame: Week 1-9 after start of radiotherapy (repeated measurement)].

CTC-AE responses are scored from 0 to 4, with 0 representing “None” and 4 representing “Very severe”.

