Duration of pain response measured by the ICPRE score will be presented graphically in separate figures. For each of the first five weeks, where daily measurements are recorded, the worst response will be used for analysis.

Mean response duration in each group will be compared using Wilcoxon rank-sum test.

I. Quality of life [Timeframe: weekly, 1-9 weeks after start of RT]: measured by EORTC-QLQ-C30 and EQ-5D-5L will be scored per instruction of the instrument and summarized for each arm. The scores will be presented graphically in separate figures. Changes in scores over time (repeated measurement) will be analyzed using Generalized Linear Mixed Models.

J. EORTC QLQ-C30, other domains [Timeframe: weekly, 1-9 weeks after start of RT]: Descriptive statistics of QLQ-C30 domains will be performed. Changes over time (repeated measurement) will be analyzed using Generalized Linear Mixed Models.

K. Weight [Timeframe: weekly week 1-9]: Changes in weight from baseline (repeated measurement) will be analyzed using Generalized Linear Mixed Models

- L. **Hospitalization:** Hospitalization rate will be calculated as days hospitalized of days alive during the 9-weeks follow-up and compared between treatment arms.
- M. **Re-irradiation rate (primary treatment site):** The results will be reported for each treatment group using time-to-event analysis (Kaplan-Meier), and differences in curves will be tested using the Log-rank test.
- N. **Overall survival** [Time Frame: Analysis will be made up to 2 years after study completion] is defined as time from inclusion until death from any cause. Overall survival will be reported off the Kaplan-Meier curves. Differences in survival curves will be tested by Log-rank test. If reached, the median survival time will be reported with a 95% confidence interval.
- O. **Analysis of correlation** between target coverage and pain response, re-irradiation (primary treatment site) and ability to walk.

Reporting of the radiation details

The following radiation details will be reported and compared between the two arms using Wilcoxon rank-sum test.

1. Delivery: VMAT, IMRT or opposing fields

2. Target doses and volumes:

- PTV V80, V90: the volume of the PTV (%) that is covered by the 80% and 90% isodose.
- CTV V80, V90: the volume of the CTV (%) that is covered by the 80% and 90% isodose
- Esophagus D0.027cm³, D1cm³, D2cm³ and D5cm³ (Gy)
- Posterior pharyngeal wall D0.027cm³, D1cm³, D2cm³ and D5cm³ (Gy)

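### Overall survival is compared by an unadjusted log-rank test with no hazard ratio, leaving out performance status, so sensitivity to a survival harm is lost

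*SAP*

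**What the plan says.** SAP, Analysis, item N reports overall survival from Kaplan-Meier curves, and "Differences in survival curves will be tested by Log-rank test". Median survival gets a 95% interval if it is reached. The SAP's section on confidence intervals and P values gives only Kaplan-Meier intervals for time-to-event outcomes, tested at 0.05 "with no adjustment for multiplicity". No Cox model, hazard ratio, stratum or covariate is named for survival anywhere, and the analysis summary table has no survival row.

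On randomisation the documents disagree:

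- Protocol 3.3: "Patients will be stratified according to performance status and fractionation scheme".
- Protocol 3.5: strata are number of fractions and treating centre.
- SAP, Allocation: "Patients are stratified by center and fractionation". The SAP's sample-size text repeats the protocol 3.3 paragraph with treating centre in place of performance status.

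On prognosis, protocol 1.1 states: "The performance status at the time of diagnosis is the main determining factor of the post-treatment outcomes". Performance status is collected at baseline (protocol section 4, Table 2). The fractionation schedule is set by the referring physician before inclusion (protocol 6.2), so it may carry prognostic information too.

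**The concern.** The experimental plan may give up target dose to spare the esophagus (protocol 6.4), and a survival difference is among the SAP's stated purposes. If a strong prognostic factor is left out of a time-to-event comparison, the unadjusted hazard ratio drifts toward 1. Patients with poor status die first, and fastest in the worse arm, so the survivors being compared become progressively less alike. A real harm is then harder to detect.

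Because item N gives no hazard ratio, a non-significant p-value would also leave the reader without any statement of how much harm has been excluded. Timing matters as well. Only patients are blinded, and the SAP lets the study group analyse secondary endpoints whenever it chooses. An adjustment added after survival by arm has been seen would not be convincing.

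**Working it through.** **The plan's own figures.** None concerns survival: no event count, hazard ratio or power is stated. The two design figures that are given do reproduce. The prior data "indicate that the rate of early esophageal toxicity with standard VMAT is 0.6", against 0.3 in the sparing arm. "The Type I error probability associated with the test of this null hypothesis is 0.05" and the null is to be rejected "with a probability (power) of 0.9". Exact two-sided Fisher power is 0.902 at 61 per arm and 0.910 at the stated 62. Simulated Wilcoxon power for ambulatory function at 66 per arm is 0.827 against the stated 84%.

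**Inputs from the documents.** 200 patients, 1:1, blocks of four and six within centre and fractionation; accrual of at most 36 months; survival analyses from 6 months after the last radiotherapy; two-year survival about 10% and median under 6 months (protocol 1.1); almost half in performance stage III-IV in the cited randomised trial (protocol 1.2).

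**Assumptions not in the documents.** Arm hazard ratio 1.5 (harm); poor performance status binary, 50%, hazard ratio 1 to 3; two equal centres; three fraction numbers split 30/30/40; two-sided 0.05; exponential survival within groups, with control two-year survival set to 10%. Each scenario has 3,000 simulated trials.

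**Power, centre and fractionation not prognostic:**

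| Performance-status HR | Control median (months) | Plain log-rank | Log-rank stratified by centre and fractionation | Cox adjusted for performance status, centre, fractionation | Mean unadjusted HR |
|---|---|---|---|---|---|
| 1 | 7.2 | 77% | 74% | 77% | 1.51 |
| 1.5 | 7.0 | 74% | 71% | 76% | 1.48 |
| 2 | 6.5 | 69% | 67% | 76% | 1.45 |
| 3 | 5.6 | 61% | 59% | 76% | 1.40 |

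The adjusted hazard ratio averages 1.51 to 1.52 throughout.

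**Centre and fractionation also prognostic.** Plain, stratified by those two factors, and adjusted Cox: 69%, 69% and 77% at performance-status HR 2; 59%, 60% and 78% at HR 3.

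**Longer minimum follow-up.** With 24 months instead of 6, at performance-status HR 2, plain against adjusted is 72% against 79%.

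**Hand check.** Schoenfeld's approximation is power = Φ(½·√d·ln HR − 1.96), with d deaths (176 to 178 in these runs).

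- HR 1.5, d = 176: ½ × 13.27 × 0.405 = 2.69; Φ(0.73) = 0.77.
- HR 1.48, d = 176: 2.60; Φ(0.64) = 0.74.
- HR 1.45, d = 177: 2.47; Φ(0.51) = 0.70.
- HR 1.40, d = 178: 2.24; Φ(0.28) = 0.61.

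Putting each shrunken hazard ratio into the formula returns the simulated power of the plain test to within a point, so the shrinkage accounts for the loss. Without any omitted factor, 80% power at HR 1.5 needs 4 × (1.96 + 0.84)² / 0.405² ≈ 191 deaths.

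**Type I error (arm HR 1).** Plain log-rank 4.5% to 5.0%; adjusted Cox 5.4% to 5.7%, with a simulation standard error of about 0.4 points.

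**Which adjustment does the work.** Stratifying by centre and fractionation alone moves power by −3 to +2 points across these scenarios. A run not tied to 10% two-year survival, with the hazard halving at each fractionation step, gained 9 points, which is an extreme case. A log-rank stratified by performance status alone gives 75% and 76% at HR 2 and 3 when centre and fractionation are not prognostic. Stratifying on all 12 cells gives 68% and 70%, because small cells waste information.

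**The case against.** The strongest reply is that the log-rank test is valid under randomisation and targets a legitimate marginal comparison. Overall survival is one of about ten secondary endpoints, without a power statement or decision rule. The documents watch for loss of effect mainly through ambulatory function (co-primary) and re-irradiation (protocol 8.3 and 9.1). All of this stands. A reader might infer that the plain test is biased under the null or invalid; the simulated type I error shows it is not, and chance imbalance in performance status is already allowed for in its error rate.

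A reader might also infer that survival is the only outcome untouched by missing diaries. The SAP's Trial design section says that re-irradiation and hospitalisation also come from treatment records.

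The size is open to challenge too. Protocol 1.1 ranks performance status first but gives no hazard ratio, and entry requires ability to complete questionnaires (protocol 5.1), which may narrow its range. With a weak effect the gain is about 2 points. In the other direction, 10% two-year survival together with a median under 6 months implies heterogeneity: a homogeneous population would have a 7.2-month median, and of the values tried with performance status as the only prognostic factor, only HR 3 brings it below 6. Nothing in the documents, however, ties that heterogeneity to performance status rather than, say, tumour type.

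Finally, protocol 3.3 might be read as meaning that performance status was balanced by design. Protocol 3.5 and the SAP agree with each other against it, so it looks like a leftover. The conflict is editorial and does not alter how survival is analysed.

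**Conclusion.** The point holds as a loss of sensitivity and of information. Item N omits the factor that the protocol ranks first, although it is recorded at baseline and, on protocol 3.5 and the SAP, was not a stratum. The plan reports no between-arm estimate.

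Against an assumed arm hazard ratio of 1.5, the plain test gives up about 2, 7 or 15 points of power when the performance-status hazard ratio is assumed to be 1.5, 2 or 3, and up to 19 if centre and fractionation also matter. An unadjusted hazard ratio, if one were reported, would average about 1.45 (performance-status HR 2) or 1.40 (HR 3). All these sizes rest on assumed prognostic effects. The direction depends only on performance status being prognostic. The co-primary analyses are not affected.

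**What to change.** In SAP item N, name as the between-arm survival comparison a Cox model with treatment arm, baseline performance status, fractionation and centre, reported as a hazard ratio with 95% CI and p-value. State how performance status is grouped. Keep the Kaplan-Meier curves, and keep the plain log-rank as supportive. Do not substitute a log-rank stratified by centre and fractionation alone, or one stratified on every combination. Add a survival row to the analysis summary, and correct protocol 3.3 to the strata actually used.

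The cost is wording: every variable is already collected. If performance status turns out not to be prognostic, almost nothing is lost (77% against 77%). The adjusted hazard ratio is conditional on the covariates and should be described that way. The change should be made before anyone sees survival by arm.

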6.4 Esophagus sparing radiotherapy vs. standard treatment

For the patients in the standard arm, a standard radiotherapy plan computed using VMAT technique aiming at covering the PTV with at least 90 % of the prescribed dose and not taking the dose to the esophagus and/or stomach into account.

For the patients in the interventional arm, a plan using VMAT technique is computed aiming at keeping the maximum dose to the esophagus and/or stomach as described in Table 4. Even if it means compromising the dose to the PTV and CTV.

Patients randomized to esophagus sparing radiotherapy needing reirradiation (**other target that primarily prescribed**) during the 9 weeks of FU, will receive esophagus sparing radiotherapy for the second target.

	Maximum Physical Esophageal Dose ($D_{0,027\text{cm}^3}$) (Gy)		Max. Esophageal Dose in EQD2 ($D_{0,027\text{cm}^3}$) (Gy), $\alpha/\beta = 3$ Gy	
Fractionation (Dosis (Gy) x Fraction)	Standard arm	Esophagus sparing arm	Standard arm	Esophagus sparing arm
5 Gy x 5	25	8,5	40	8
3 Gy x 10	30	10	36	8
10 Gy x 1	10	5	26	8
8 Gy x 1	8	5	17,6	8

Table 4. Maximum esophageal dose. Standard arm vs. esophagus sparing arm.

7 HbA_{1c} and Flash glucose monitoring

HbA_{1c} will be measured at baseline, which is standard procedure in one of the participating centers.

²³ In order to obtain ambulatory glucose profiles for retrospective glucose data analysis we will use a blinded professional sensor-based Flash glucose monitoring system (FreeStyle Libre Pro™; Abbott Diabetes Care, Witney, UK).^{19,20} The sensor is worn on the upper arm for 14 days. The sensor is factory calibrated which means that, after activating the sensor at baseline, no further intervention during the 14-day wear is required. As the sensor is blinded, data are not visible to participants or investigators during sensor wear. The sensor automatically captures and stores glucose data every 15 min (96 glucose readings/day). After 14 days the sensor is dismantled, and glucose data are wirelessly transferred to the pro-reader. Summary glucose reports are generated using the system software. Patients in our study will be followed for 28 days after start of radiotherapy treatment requiring one sensor change. This will include time without glucocorticoid treatment.

The patients participating in this part of the study will not be subject to standard glucose measurements; instead they will be thoroughly instructed to contact the PI if symptoms of hyperglycaemia should occur.

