9.2 Toxicity

Toxicity reports from palliative radiation for MSCC are scarce, as most studies focus on evaluating effectiveness of treatment.^{6-8,10} Considering this, treatment is generally well tolerated.

In a retrospective review of 1304 patients evaluating prognostic factors for different radiation schedules, Rades et al found no relevant acute or late toxicity.⁸ In another study of 324 patients by Rades et al acute radiation-related toxicity did not exceed grade 1 according to Common Terminology Criteria for Adverse Events version 3.0. No late toxicity was reported.⁶

In a randomized trial investigating the clinical outcome and toxicity of two different hypofractionated RT regimens Maranzano et al found grade 3 esophagitis in 1,5% of the patients and grade 3 vomiting or nausea in 6% of the patients. Grade 1-2 oral or esophagus dysphagia occurred in 14%. Late toxicity was never recorded.¹⁰

In the SCORAD trial Hoskin et al randomized 686 patient with MSCC between two RT regimens (8 Gy x 1 vs 4 Gy x 5).⁷ Grade 1-2 adverse events occurred in 51,9%-56,9% of the patients. Most frequently

reported toxicities were fatigue, skin radiation reaction, anorexia, pain, nausea and diarrhea. Grade 3-4 events occurred in approximately 20,5% of the patients, dominated by fatigue, pain and respiratory symptoms. In contrast to other studies ESO-SPARE patients will be irradiated using VMAT technique only. ^{6-8,10} This enables us to shape the dose gradient more smoothly around target avoiding large radiation fields. ESO-SPARE only includes patients irradiated above Th12, therefore we do not expect any cases of treatment related diarrhea.

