- The volume of esophagus and posterior pharyngeal wall (% and cm³) receiving more dose than the prescribed constraint
- Selected OAR will be presented (e.g., Spinal Cord D0.027cm³, D0.5cm³, lung V20 and V5)

Double included patients

The ESO-SPARE protocol allowed participants to be included twice at the discretion of the treating oncologist. Double included participants were excluded at the second entry for time-to-event analyses (survival) and the quality-of-life analyses. For radiation details analyses, all lesions will be included.

Missing data

- We will report the numbers and proportions of missing data in each trial arm including:
 - Number of participants who have died.
 - Number of surviving participants with missing data.
 - The proportion of participants with partly completed questionnaires and the proportion of item-level missing data at each timepoint.
- Reasons for missing data will be collected for all randomized patients and reported for each trial arm.
- The assumed missing data mechanism will be reported for all primary and secondary outcome measures. For each outcome missing data will be categorized as.
 - a. Missing completely at random – when missingness is nothing to do with the participant.
 - b. Missing at random – when missingness is related to the participant and can be predicted from other information about them.
 - c. Missing not at random – when missingness is specifically related to the data that are missing.
- We will provide a detailed comparison of the characteristics of those with observed and missing data before and after the interim analysis (1).
- In case of non-complete reporting of measurements, the following assumptions are made:

If the NPRS score is not given, but the patient is described without any pain and take no analgesic medication, the NPRS score is set to zero. All other cases, the NPRS is recorded as “not available”.
- Where missing data is present, secondary sensitivity analysis using multiple imputation and model-based methods assuming that data are missing not at random may be performed.

Statistical software

All statistic calculations will be performed using SPSS (SPSS Inc, Illinois, USA) and R statistics (RCRAN).

Analysis summary

Outcome	Instrument/Method/Unit	Timeframe	Data type	Statistical analysis
Primary Peak dysphagia	NCI-PRO-CTC-AE	Within five weeks after start of radiotherapy	Ordinal	Wilcoxon rank-sum test

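### SAP radiation details (low severity): the rank-sum test is applied to an unordered delivery technique, and the dose threshold for the volume comparison is not written out

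*SAP*

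**What the plan says.** The SAP section Reporting of the radiation details opens with one rule for all its items: "The following radiation details will be reported and compared between the two arms using Wilcoxon rank-sum test". Item 1 is "Delivery: VMAT, IMRT or opposing fields". Item 2 holds the continuous dose and volume measures: PTV and CTV coverage, oesophagus and posterior pharyngeal wall D0.027cm³ to D5cm³, and "The volume of esophagus and posterior pharyngeal wall (% and cm³) receiving more dose than the prescribed constraint". No Gy value, arm or table is named for that constraint. The Analysis summary at the end of the SAP gives rank-sum for dosimetry parameters, typed as continuous, and gives no separate method for delivery technique.

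The protocol bears on this in three places.

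- Section 9.2 states that "ESO-SPARE patients will be irradiated using VMAT technique only", and section 6.4 plans VMAT in both arms.
- Section 6.4 says that standard-arm plans are made "not taking the dose to the esophagus and/or stomach into account". Only the interventional arm plans towards the Table 4 maximum for oesophagus and/or stomach.
- Table 4 ("Maximum esophageal dose. Standard arm vs. esophagus sparing arm") nevertheless prints a physical-dose column for each arm: 25, 30, 10 and 8 Gy for standard, and 8.5, 10, 5 and 5 Gy for sparing.

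**The concern.** Two items in the list cannot be carried out safely as written.

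First, a rank-sum test needs an order. VMAT, IMRT and opposing fields have none, so the analyst must invent a numbering, and with three categories the result follows from that choice.

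Second, the volume item depends on a threshold that the SAP does not state, while Table 4 has two columns. If an analyst took each arm's own column, the standard-arm threshold would be the full prescribed dose. Almost no volume could exceed it, whatever dose the oesophagus received. For the posterior pharyngeal wall there is no value to take from either document.

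What is at stake is the account of whether the two arms received different treatment as intended. The trial's efficacy conclusions do not depend on these items.

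**Working it through.** **1. Delivery technique.** The documents give no counts, so these are assumed, per 100: standard 85/5/10 and sparing 80/18/2 (VMAT/IMRT/opposing fields).

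Chi-square: expected counts per arm are 82.5, 11.5 and 6. The statistic is 2 × (2.5²/82.5 + 6.5²/11.5 + 4²/6) = 0.15 + 7.35 + 5.33 = 12.83 on 2 df, p = 0.0016. It does not depend on numbering.

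Rank-sum: U counts the standard-versus-sparing pairs in which standard has the higher code, plus half the ties. Half the ties is (85×80 + 5×18 + 10×2)/2 = 3455 under any numbering. The null mean is 100×100/2 = 5000. The tie-corrected variance uses pooled counts 165, 23 and 12: (10000/12) × [201 − 4505820/39800] = 73157, SD 270.5.

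| Numbering | U | z | p |
|---|---|---|---|
| VMAT 1, IMRT 2, opposing 3 | 5×80 + 10×98 + 3455 = 4835 | −0.61 | 0.54 |
| VMAT 1, opposing 2, IMRT 3 | 10×80 + 5×82 + 3455 = 4665 | −1.24 | 0.22 |
| IMRT 1, VMAT 2, opposing 3 | 85×18 + 10×98 + 3455 = 5965 | 3.57 | 0.0004 |

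Reversing a numbering only changes the sign of z, so three p-values cover all six numberings.

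Two techniques only (assumed 90/10 versus 100/0): chi-square is 2 × (5²/95 + 5²/5) = 10.53, p = 0.0012. The squared rank-sum z is this multiplied by (N − 1)/N = 199/200, giving 10.47, p = 0.0012 under every numbering. So the problem exists only if all three techniques occur.

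**2. Table 4.** The EQD2 column reproduces from D × (D/n + 3)/5:

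- Standard: 25×8/5 = 40; 30×6/5 = 36; 10×13/5 = 26; 8×11/5 = 17.6.
- Sparing: 8.5×4.7/5 = 7.99; 10×4/5 = 8; 5×8/5 = 8 for both single fractions.

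The standard physical doses equal the total prescribed doses in Table 3. The standard-to-sparing ratios are 25/8.5 = 2.9, 30/10 = 3.0, 10/5 = 2.0 and 8/5 = 1.6. Within one fractionation EQD2 rises with physical dose, so the volume above the sparing value is the same on either scale, apart from the rounding of 7.99 to 8.

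**3. Consequence of the threshold choice, 3 Gy × 10.** This is a simulation of 1,000 runs per setting. All shapes are assumed: 66 patients per arm, oesophagus 8–15 cm³, dose rising linearly from 0 to its maximum, standard maximum 30 Gy (SD 1), sparing maximum with the mean shown (SD 1.5). The volume above threshold T is volume × (max − T)/max, or 0 if negative.

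| Mean sparing maximum | Own column (30 vs 10 Gy) | Common 10 Gy |
|---|---|---|
| 9 Gy | sparing significantly better 52%, no difference 48% | sparing better 100% |
| 10 Gy | sparing significantly worse 48%, no difference 52% | sparing better 100% |
| 11 or 12 Gy | sparing significantly worse 100% | sparing better 100% |

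Mean volumes explain this. Standard has about 0.15 cm³ above 30 Gy but about 7.7 cm³ above 10 Gy. Sparing has about 0.2 to 1.8 cm³ above 10 Gy.

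**4. Posterior pharyngeal wall.** Table 4 and section 6.4 cover oesophagus and/or stomach. Section 6.3 refers to local guidelines for dose constraints in general, but the SAP does not point to them, and neither document prints a value for this structure.

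**The case against.** The plan has a fair defence on each part.

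- **Threshold.** A reader might infer that the SAP compares the arms against two different limits and is therefore biased against sparing. The documents do not support that. Standard plans ignore oesophageal dose, and the standard column only restates the prescription. The sparing-arm value is thus the only constraint anyone plans to, and the natural meaning of the phrase. With that value used in both arms the comparison is sound. This stands: what is missing is a sentence, not a correct method. Nor are the columns uniformly three-fold apart; the ratios run from 1.6 to 3.0.
- **Other evidence.** Oesophagus D0.027cm³ to D5cm³ are compared in Gy with no threshold, and D0.027cm³ is the metric used in Table 4. A misleading volume result would sit beside these. This also stands.
- **Technique.** The protocol plans VMAT throughout, so three techniques may never occur. The summary row types the dosimetry items as continuous, which suggests that technique was swept into the rank-sum sentence by loose drafting. Both are plausible, but the sentence still covers item 1 and nothing else in the SAP replaces it.

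A reader might also infer from the technique list that some sparing-arm patients were treated with opposing fields, with which protocol section 1.2 says sparing is not possible. The SAP only names categories to be reported; it gives no counts, so this cannot be concluded.

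**Conclusion.** The point holds at low severity, in three parts.

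- The stated test for delivery technique is wrong for an unordered variable. It matters numerically only if all three techniques occur; on the assumed counts the p-value then runs from 0.0004 to 0.54.
- The volume threshold is an ambiguity with a clear natural reading. The comparison reverses only if an analyst uses each arm's own column. The size of that reversal rests on the assumed dose-volume shapes; its direction follows from the standard column being the full prescribed dose.
- The pharyngeal-wall version cannot be computed from the two documents as they stand.

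These are reporting items. Neither co-primary endpoint, no listed secondary endpoint, and no sample size or power figure is affected. The thresholdless oesophageal dose measures remain valid evidence of what was delivered.

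**What to change.** Amend the SAP section Reporting of the radiation details as follows.

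1. Restrict the rank-sum sentence to the continuous dose and volume items.
2. Report delivery technique as counts per arm, with Fisher's exact test (in its form for more than two categories) or chi-square. The same table shows how many in each arm were treated with something other than VMAT.
3. Reconcile the three listed techniques with the VMAT-only statement in protocol section 9.2.
4. State that the constraint, used purely as an analysis threshold in both arms, is the sparing-arm value of protocol Table 4 for the patient's fractionation.
5. For the posterior pharyngeal wall, name the reference value used for analysis and its source, or drop that item.

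The cost is a few lines of text. No new data are needed and no treatment plan changes.
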